1.3.1. Primary Outcome Measures

The primary outcome measure is the effect of sensory **flicker** exposure on local field potential (LFP): comparing mean power spectral density at the frequency of flicker being presented between flicker and baseline periods. [Time Frame: Up to 6 weeks]

Power spectral density of the LFP will be measured across stimulus frequencies and modalities of sensory flicker stimuli in visual areas, auditory areas, hippocampus and prefrontal cortex. The mean power spectral density measured in dB at the frequency of flicker being presented will be compared between flicker stimulation and no-stimulation baseline periods.

1.3.2 Secondary Outcome Measures:

The secondary outcome measure is the effect of sensory flicker on interictal epileptiform discharges (IEDs), which represent pathological activity often observed in epilepsy [Time Frame: Up to 6 weeks]

The effect of the sensory flicker will be evaluated by the comparison of the whole-brain rate of IEDs between sensory flicker stimulation and baseline (no stimulation).

1.3.3 Exploratory Outcome Measures:

- 1) To study whether sensory flicker exposure can entrain LFPs and modulate single neuron activity in higher cognitive areas such as the hippocampus and prefrontal cortex.
- 2) To identify the modality and frequency of flicker to which given brain regions are most efficiently modulated at the LFP and the single unit levels.
- 3) To identify potential effects of audiovisual flicker on various cognitive processes through a behavioral task.
 - a. If there are effects, to identify their electrophysiological correlates (such as changes in sharp-wave ripples' rate).
- 4) To compare the effects of sensory flicker modulation to direct electrical modulation of various neural circuits within individual subjects.

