- Frequencies: random, or anywhere from 3Hz to 200Hz.

Additionally, subjects may be exposed to individual pulses of light and/or sound, i.e. around or less than 1 pulse /second, for up to 20 minutes at a time.

For experiments characterizing neural response to sensory flicker, patients may be exposed for about 10 minutes to a single modality and frequency combination, such as 40Hz (gamma-like) audiovisual flicker, 5.5Hz (theta-like) audiovisual flicker, or random audiovisual flicker.

For one of the experiments testing the effects of sensory flicker on memory, patients may be exposed to audiovisual flicker for up to about 36 minutes at a time.

For another experiment, patients may be exposed to audiovisual flicker of a given frequency or random frequency, at modalities of visual only, auditory only, or audiovisual combined, for up to 1h at a time.

For another experiment testing the effects of sensory flicker on memory, patients may be exposed, eyes open, to visual flicker via a strip of LEDs secured to the perimeter of a monitor screen that presents images or words, or via wearing a customized DAVID device with glasses that have view holes; sound stimulus will be again provided via earbuds or headphones. In this experiment, sensory flicker would last for a few seconds at a time.

For other experiments testing the effects of sensory flicker on memory or interictal epileptiform discharges, patients may be exposed, eyes open, to visual and/or auditory flicker, anywhere from 10s to 60 minutes at a time, while performing on a spatial navigation task (see more details below). Visual flicker will be administered via customized DAVID device with glasses that have view holes, and auditory flicker will be administered via earbuds or headphones.

For most to all experiments involving exposure to visual and/or auditory stimuli, there will be an occluded condition. In this occluded condition, the subject will wear a sleeping mask or towel on their eyes (under the LED glasses mentioned above), and commercially available earplugs; in this condition, they will be exposed to similar visual and/or auditory stimuli as in the non-occluded condition. Subjects will be instructed on how to properly wear earplugs by specifying instructions similar to the ones available here: <https://www.cdc.gov/niosh/mining/content/earplug.html>.

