2.2.5. Spatial Navigation Experiments

We have preliminary data showing that sensory flicker may decrease the rate of interictal epileptiform discharges (IEDs), which constitute abnormal brain activity often detected in epilepsy patients. In the following experiments, we will further test the effects of sensory flicker on the rate of interictal epileptiform discharges, while the patient performs a spatial navigation task described below. The simultaneous running of the spatial navigation task will be used to control for subject's attention and arousal state, which has been shown to influence the rate of IEDs.

Spatial navigation task:

In this task, subjects learn the layout of a computer-generated virtual city environment and the locations of landmarks by navigating from a first-person perspective using a game controller or keyboard⁴³. Each session (virtual day) of the task consists of 12 virtual city environments where subjects navigate for 9 minutes. There are hidden shortcuts to goal landmarks where subjects learn to find as they are instructed to navigate to goal landmark as quickly as possible. Behavioral records from the memory testing (e.g. keystrokes, in the form of game controller or keyboard inputs) will be collected.

During these experiments, the patient will do the spatial navigation task above while being exposed to sensory flicker via glasses lined with LEDs with see-through holes, and earbuds or headphones. Subjects may be exposed, up to 60 minutes at a time, to visual and/or auditory flicker at frequencies anywhere between 3-200Hz.

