4. PARTICIPANT RECRUITMENT

We aim to include, across all experiments, about 100 adult patients (most patients will only participate in one or a few of the experiments) with pharmaco-resistant epilepsy in whom intracranial depth or grid/strip electrodes are implanted in order to determine the area of seizure onset for possible surgical resection. We anticipate having access to an adequate sample size to attain significant preliminary data in one year. Between two neurosurgeons, our center implants >50 epilepsy patients per year for intracranial monitoring. Approximately 90% of these patients will meet all inclusion criteria.

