5. STATISTICAL ANALYSIS

For objectives 1 and 2, we will perform analyses similar to the ones used in Martorell et al.'s study². We will perform a power spectral density analysis of LFP signal in function of frequency and modality (visual, auditory or audiovisual) of the sensory flicker stimulus, using multi-taper methods. Comparisons will be drawn between the mean power spectral density under a given condition and control (random sensory flicker or no flicker) condition, using the Wilcoxon rank-sum test with Bonferroni correction for multiple comparisons. To analyze firing rate modulation of single units to sensory flicker, we will produce a histogram of each single unit's firing rate

aligned to the onset of light and/or sound stimulus. Moreover, we will analyze how strongly the firing rate of single units is phase-locked to the stimulus being played, by calculating and comparing the vector strength of their firing rate modulation under different conditions, using the Kolmogorov-Smirnov test.

For objective 3, we will use similar methods as mentioned above, and compare the effect size of LFP entrainment and firing rate modulation in different brain regions, in function of various sensory flicker parameters (i.e. frequency and modality).

For objective 4, we will do within-subject comparison of the rate of interictal epileptiform discharges during various stimulation and/or baseline conditions. If normally distributed we will use t-test to compare the conditions, otherwise we will use repeated-measures ANOVA.

For objective 5, memory performance will be compared with a repeated-measures ANOVA across the different conditions (e.g. for example, 5.5Hz or 40Hz audiovisual flicker vs. random audiovisual flicker). For one of the memory experiments, performance in the case of random flicker will serve as the baseline from which we will infer any improvement or impairment in memory performance.

All neural data analyses will be performed in Python and/or MATLAB.

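### For the secondary IED outcome, the fallback named for non-normal data, repeated-measures ANOVA, assumes normality too, and for a paired flicker-versus-baseline contrast with one rate per patient per condition it reproduces the t-test's p-value

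*Combined protocol and SAP*

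**What the plan says.** Section 1.3.2 defines the secondary outcome as a two-condition contrast: "comparison of the whole-brain rate of IEDs between sensory flicker stimulation and baseline (no stimulation").

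Section 5 gives the method under objective 4: "we will do within-subject comparison of the rate of interictal epileptiform discharges during various stimulation and/or baseline conditions". The rule for choosing the test follows: "If normally distributed we will use t-test to compare the conditions, otherwise we will use repeated-measures ANOVA". The objective numbers in section 5 do not match a numbered list elsewhere, but the text of objective 4 is plainly about IEDs.

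No other section gives a method for IEDs. The only rank test in section 5 for a rate or power comparison, the Wilcoxon rank-sum test with Bonferroni correction, is assigned to LFP power spectral density. For objective 5 the plan uses the same ANOVA with no normality condition: "memory performance will be compared with a repeated-measures ANOVA across the different conditions".

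The plan does not say that the t-test is paired, which quantity is checked for normality (the rates or the paired differences), how it is checked, or how many values each patient contributes per condition.

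**The concern.** The authors foresaw that IED rates might not be normal and wrote a step for that case. The step replaces one normal-theory method with another. Repeated-measures ANOVA rests on normal errors and, with three or more conditions, on sphericity as well. What properly separates a paired t-test from repeated-measures ANOVA is the number of conditions, not the shape of the distribution.

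Two things are at stake. An analyst who finds skewed rates has no usable instruction, which leaves room for a choice of method after the data are seen. And if rates vary widely between patients, the few with very high rates dominate the variance of the raw differences, so a real effect can be missed. The primary LFP outcome is not affected.

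**Working it through.** The documents state no power, effect size or sample size for the IED analysis, so there is no figure of the plan's own to reproduce. The check has two parts.

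**1. The identity (algebra, no distributional assumption).** Inputs: two conditions (section 1.3.2), within-subject comparison (section 5), and one rate per patient per condition (assumed). Let dᵢ be patient i's flicker rate minus baseline rate, with mean d̄ and standard deviation s over n patients.

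- Paired t-test: t = d̄ / (s/√n), so t² = n·d̄²/s².
- Repeated-measures ANOVA: SS(condition) = n·d̄²/2 on 1 df; SS(error) = (n − 1)·s²/2 on n − 1 df.
- F = (n·d̄²/2) / (s²/2) = n·d̄²/s² = t². F on (1, n − 1) df has the same p-value as two-sided t on n − 1 df.

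Numerical confirmation on simulated log-normal rates:

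| n | t² | F | p, paired t | p, RM-ANOVA | p, signed-rank |
|---|---|---|---|---|---|
| 10 | 2.4971 | 2.4971 | 0.14851 | 0.14851 | 0.131 |
| 20 | 2.0677 | 2.0677 | 0.16672 | 0.16672 | 0.216 |
| 50 | 0.6458 | 0.6458 | 0.42551 | 0.42551 | 0.020 |
| 100 | 0.1809 | 0.1809 | 0.67154 | 0.67154 | 0.013 |

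Over 300 further skewed data sets (n from 5 to 59) the largest difference between the t and ANOVA p-values was 6e-15, which is rounding.

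Where the identity stops: in a three-condition example (n = 20) the ANOVA omnibus p was 0.642 and one pairwise t-test gave 0.293. An unpaired t-test on the n = 50 data gave 0.628 instead of 0.426.

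**2. Size of the possible power loss (illustrative; all distributional inputs assumed).** Model: Poisson IED counts; log-normal patient rates with median 5 or 0.5 per minute and between-patient log SD 0.3 to 1.2; within-patient log SD 0.3 per period; a true 20% reduction; 10-minute periods; N = 20, 40 or 100; two-sided 0.05; 4,000 runs per setting (standard error at most 0.8 points). Signed-rank zeros are handled by the Pratt method.

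| N | Median rate/min | Between-patient log SD | Paired t | Signed-rank | Gain (points) |
|---|---|---|---|---|---|
| 40 | 5 | 0.3 | 79% | 79% | 0 |
| 40 | 5 | 0.5 | 73% | 77% | +4 |
| 40 | 5 | 0.8 | 63% | 74% | +11 |
| 40 | 5 | 1.2 | 47% | 72% | +25 |
| 40 | 0.5 | 0.3 | 41% | 39% | −2 |
| 40 | 0.5 | 1.2 | 34% | 42% | +8 |
| 20 | 5 | 0.3 | 48% | 48% | 0 |
| 20 | 5 | 1.2 | 25% | 42% | +17 |
| 100 | 5 | 0.3 | 99% | 99% | 0 |
| 100 | 5 | 1.2 | 80% | 98% | +18 |

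Over all 24 settings the gain runs from −2 to +25 points.

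Period length matters, because section 2.2.4 allows flicker "anywhere from 10s to 60 minutes at a time". At N = 40, 5 per minute, log SD 1.2, t versus signed-rank is 14.4 / 15.2% at 10 seconds, 32 / 41% at 1 minute, 45 / 66% at 5, 50 / 77% at 30 and 48 / 78% at 60.

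Type I error over the 24 null settings (10,000 runs each) was 0.032 to 0.057 for the planned test and 0.046 to 0.056 for signed-rank.

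A paired t-test on log rates (0.5 added to counts) is sometimes better and sometimes worse than signed-rank. At N = 40 and log SD 1.2 it has 87% against 78% at 5 per minute over 60 minutes, but 33% against 42% at 0.5 per minute over 10 minutes.

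With three conditions (reductions 0/10/20%, N = 40, 5 per minute), raw-rate repeated-measures ANOVA has power 69% at log SD 0.3, 53% at 0.8 and 36% at 1.2.

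**The case against.** **The ANOVA was meant for three or more conditions.** This is plausible, since section 5 speaks of the "rate of interictal epileptiform discharges during various stimulation and/or baseline conditions". But the sentence ties the choice to normality. If the number of conditions was intended, the rule still needs rewriting, and the ANOVA would still assume normality.

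**The identity may not apply.** This stands as a limit. Section 2.2.4 describes sequences of trials lasting seconds to 5 minutes, section 4.4 allows more than one session, and the t-test is not called paired. A reader might infer that the fallback can never change the result of the secondary contrast. The documents do not support that, because they do not fix one value per patient per condition. What holds in every case is that the fallback does not address non-normality.

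**The t-test is robust.** On validity this stands: simulated type I error was near nominal or below it. A reader might infer a raised false-positive risk; nothing here supports that.

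**The loss of power is assumed.** This also stands. Section 4 gives only a total, "across all experiments, about 100 adult patients (most patients will only participate in one or a few of the experiments"), and no IED distribution appears anywhere. A reader might infer that the trial will lose 25 points of power; that is the extreme of an assumed range that includes zero and slightly negative gains.

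**Signed-rank is a preference.** Partly right. The log-rate results show that no single test is best in every setting, so signed-rank is a default, not the only acceptable choice.

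**Conclusion.** The rule is wrong as written and should be corrected. That repeated-measures ANOVA is no remedy for non-normality is certain and needs no simulation. That it returns the same p-value as the t-test is also certain, given a paired test, two conditions and one rate per patient per condition.

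The consequence is moderate. The outcome is secondary and the documents claim no IED power. The sure effect is an instruction that does not do its job. The loss of power is conditional on wide between-patient differences in rate and on observation periods long enough for those differences to dominate counting noise. Section 2.2.5 says "We have preliminary data showing that sensory flicker may decrease the rate of interictal epileptiform discharges", so the investigators can check which setting applies.

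**What to change.** Delete the normality switch for objective 4 and replace it with wording to this effect:

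> Whole-brain IED rate is the IED count divided by recording time, one value per patient per condition. Flicker is compared with no-stimulation baseline within patient by the Wilcoxon signed-rank test on the paired rate differences, with zero differences handled by the Pratt method. This test is fixed before analysis. The mean paired difference and its 95% confidence interval are reported beside it. With three or more conditions, each flicker condition is compared with baseline by the same test with Bonferroni correction; if an omnibus test is wanted, repeated-measures ANOVA on log rates is a supporting analysis.

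A paired t-test on log rates (0.5 added to counts) is an acceptable alternative as the deciding test if the preliminary IED data support it, provided the choice is written down before analysis.

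The change needs a few sentences and no new data. Its costs are:

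- **Power if the differences are normal:** about 2 to 3 points. Simulated t versus signed-rank: 80.3 vs 78.3% at N = 20, 79.4 vs 77.6% at N = 40, 80.0 vs 78.0% at N = 100.
- **Target of the test:** signed-rank tests symmetry of the differences about zero, not a zero mean. With skewed differences whose mean is zero it rejects more often than the t-test. This must be stated, and it is why the mean difference is reported as well.
- **Multiplicity:** Bonferroni correction lowers the power of each comparison when several flicker conditions are tested. The plan already accepts this for the LFP analysis.

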2.2.2. Monitoring participants

The epilepsy monitoring unit (EMU) at Emory University Hospital is a 10-room inpatient ward that is designed for inpatient video-EEG monitoring and is staffed by a multidisciplinary team of specialists, including attending physicians, fellows, psychiatrists, EEG technicians, nurses, and information-technology technicians from the Emory Healthcare Information Services (EHc-IS). The EMU contains 10 computers with monitors, one station per room, to visualize the real-time recording of EEG and video data. The data is automatically stored on a server in the EMU for secure storage and access. The EMU continuously monitors the daily progress and health of each patient server for secure storage and access. The EMU rotates personnel to monitor and care for each patient daily (24 hours per day) during the patient's stay (on average 2-3 weeks) in the EMU. A patient under presurgical evaluation is discharged from the EMU at the discretion of the treating physicians. Patients are discharged generally after 5 weeks with no seizures or if the patient has had at least 3-5 reliable seizures with ostensibly focal epileptic activity according to the EEG.

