2.2.8. Memory consolidation experiment

To determine whether audiovisual flicker impacts memory consolidation, subjects may go through the following experimental paradigm or a similar one, based on Roberts et al.'s (2018)¹³ experiment (Figure 5).

Patients will view 4 series of words or images. In 2 of these series, they will be asked for each word or image whether it refers to a living thing, while in the other 2 series, they will be asked whether each word or image refers to something that is man-made. This will be followed by a 36-minutes period of exposure to audiovisual flicker (either random or 5.5Hz or 40Hz, via the customized DAVID device). Finally, they will undergo an unexpected test of memory for the words or images they've been exposed to (item recognition), as well as the associated contextual sorting they had to perform (alive vs man-made, i.e. source recognition).

For this experiment, depending on his or her choice, a patient may go through the task more than once on different days, being exposed to a different condition each time (random, 5.5Hz, or 40Hz audiovisual flicker). This would allow us to compare the effects of specific frequencies of audiovisual flicker on memory, in the same patients.

[figure not shown]

Figure 5: experimental paradigm from Roberts et al. (2018). In our experiment, we may use images instead of words, and patients will be tested for effects of either random, 5.5Hz or 40Hz audiovisual flicker on memory. In case a patient were to be tested for the effects of more than one type of sensory flicker, he or she would be tested for each type of sensory flicker on different days.

The anticipated duration of this experiment is about 120min for each day.

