4.4. Study timelines

We anticipate that each recruited subject will participate in one or more experimental sessions (if and when the patient is agreeable to do so) during the 2-4 weeks while they are in the hospital being investigated by the clinical team for intracranial seizure localization.

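### In the memory consolidation experiment patients choose how many condition-days to do, but the named repeated-measures ANOVA in its standard form uses only patients with every condition

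*Combined protocol and SAP*

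**What the plan says.** Section 2.2.8 gives one flicker condition per visit (random, 5.5Hz or 40Hz). Each visit takes about 120 minutes, and different conditions fall on different days. Repeat visits are optional: "depending on his or her choice, a patient may go through the task more than once on different days". Section 4.4 expects one or more sessions per patient, "if and when the patient is agreeable to do so". Section 4.5 allows withdrawal after consent.

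For memory, which Section 5 numbers objective 5, the analysis is: "memory performance will be compared with a repeated-measures ANOVA across the different conditions". The example given there sets 5.5Hz or 40Hz against random flicker. For one of the memory experiments, random flicker is named as the baseline.

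Section 5 defines no analysis population and no rule for a patient with only some of the conditions. Section 2.2.12 covers retrieval of missing records, which does not help with a condition that was never run. Section 6.2 permits data collected before withdrawal to be used, but names no method for using them.

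**The concern.** A patient with one or two consolidation conditions is an ordinary outcome of this design. The named analysis is built for the opposite case, where every patient contributes every condition. Followed as written with standard software, it leaves the analyst two choices: set aside the incomplete patients, or pick another method once the data are in hand.

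Two things are at stake. The first is precision, since sessions from a scarce intracranial population would be collected and not used. The second is whom the result describes. Patients who return for three long visits may differ from those who stop in how well they tolerate flicker or how they respond to it.

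**Working it through.** The plan has no figure to reproduce. It gives no per-experiment sample size, stopping rate, variance, correlation, effect size or power. Section 4 gives only about 100 patients across all experiments. Every input below is therefore an assumption, chosen to show a range.

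**1. What the standard test does with incomplete sets.** A standard Python repeated-measures ANOVA routine (AnovaRM in statsmodels) was run on 10 patients and three conditions with two cells removed. It stopped with an error that the data were unbalanced.

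**2. How many sets would be complete.** Let s be the chance of stopping after each of the first two sessions.
- Share with all three conditions = (1−s)².
- Share of collected sessions unused by a completer analysis = [s + 2s(1−s)] / [s + 2s(1−s) + 3(1−s)²].
- Example, s = 0.3: 0.7² = 49% complete; (0.30 + 0.42)/(0.30 + 0.42 + 1.47) = 33% of sessions unused.

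| s | 0.1 | 0.2 | 0.3 | 0.4 | 0.5 |
|---|---|---|---|---|---|
| All three conditions | 81% | 64% | 49% | 36% | 25% |
| Sessions unused | 10% | 21% | 33% | 45% | 57% |

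**3. Precision of a contrast between two conditions.** Take score variance 1, correlation ρ between a patient's sessions, and n3/n2/n1 patients with three/two/one conditions, balanced over conditions.
- Three-condition completers: variance = 2(1−ρ)/n3.
- Pairwise completers (patients with both conditions): variance = 2(1−ρ)/(n3 + n2/3).
- All sessions, generalised least squares: variance = 2/a, where a = n3/(1−ρ) + n2(2+ρ)/[3(1−ρ²)] + n1/3.

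At ρ = 0.5 the three values of a are:
- 10/9/9: 20 + 10 + 3 = 33
- 6/12/12: 12 + 13.33 + 4 = 29.33
- 15/9/6: 30 + 10 + 2 = 42

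| Mix | Completers | Pairwise | All sessions | SE cut v completers | SE cut v pairwise |
|---|---|---|---|---|---|
| 10/9/9 | 1/10 = 0.1000 | 1/13 = 0.0769 | 2/33 = 0.0606 | 1−√0.606 = 22% | 1−√0.788 = 11% |
| 6/12/12 | 1/6 = 0.1667 | 1/10 = 0.1000 | 2/29.33 = 0.0682 | 1−√0.409 = 36% | 1−√0.682 = 17% |
| 15/9/6 | 1/15 = 0.0667 | 1/18 = 0.0556 | 2/42 = 0.0476 | 1−√0.714 = 15.5% | 1−√0.857 = 7% |

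For 10/9/9, all sessions are worth 33/2 = 16.5 complete patients. For correlations of 0.3 to 0.7 the cut against three-condition completers runs from 14% to 39%. These figures exclude the session-order term, which gives back a small part of the gain.

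Power for a 0.6 SD difference in the 10/9/9 mix is Φ(0.6/SE − 1.96):
- Completers: SE 0.316, 48%
- Pairwise completers: SE 0.277, 58%
- All sessions: SE 0.246, 68%

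The normal approximation flatters numbers this small. An exact paired t-test on 10 patients gives 40%, not 48%.

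**4. Bias.** A simulation used 60 patients, 150 runs, random condition order, no order effect, a true mean effect of 0.30 that varied between patients (SD 0.8), and about 48% completers. The mixed model had a patient intercept and condition only.

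| Why patients stop | Completers | Mixed model, all sessions |
|---|---|---|
| At random | 0.29 | 0.29 |
| After a poor observed score | 0.41 | 0.37 |
| Driven by the patient's own benefit | 0.73 | 0.57 |

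Under random stopping the spread of the estimate was 0.25 for completers and 0.20 for the mixed model. Data are lost in every row. Bias depends on the reason for stopping, and the mixed model reduces it without removing it.

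**The case against.** The strongest reply is that the plan never says incomplete patients are discarded. A reader might infer such a rule, but the documents are silent; the loss follows from the standard form of the test. Section 5's example can also be read as separate comparisons of each frequency with random flicker. On that reading a patient with random plus one frequency is analysed, and the relevant gain is the smaller one, 7-17%. This stands, and both comparators are therefore shown. It does not rescue a patient with one condition, or one with 5.5Hz and 40Hz but no random session.

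A reader might extend the point to interictal discharges. The documents do not support that. Section 5 says "If normally distributed we will use t-test to compare the conditions, otherwise we will use repeated-measures ANOVA", so ANOVA is only the fallback there. The secondary outcome (1.3.2) is flicker against a no-stimulation baseline, and nothing places those two conditions on separate days. Loss of a condition is possible but not shown.

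Nor does the point reach the same-session comparison in the encoding task (2.2.7). Flicker accompanies some items within one study phase, so one session yields both conditions. Stopping early can lose only the next-day test.

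A reader might also infer a known bias, for example because discharge can follow "if the patient has had at least 3-5 reliable seizures with ostensibly focal epileptic activity according to the EEG". Section 2.2.2 leaves discharge to the treating physicians and also describes it after 5 weeks without seizures. Nothing links seizure count to memory response, so direction and size stay unknown.

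Finally, the magnitudes are illustrative, and memory is an exploratory outcome (1.3.3). Both are true. They limit the weight of the point without removing it.

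**Conclusion.** The point holds for the consolidation experiment under objective 5, and only there. Voluntary condition-days make incomplete sets expected, the named test in its standard form cannot use them, and no rule covers them.

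Under a correlation of 0.5 and the three assumed mixes, using all sessions cuts the standard error of a pairwise contrast by about 15-36% against three-condition completers and 7-17% against pairwise completers, before the session-order term. The true gain depends on how many patients stop, which the documents do not say. If nearly all patients completed three days, it would be negligible. Selection bias is a possibility, not a finding. Because the outcome is exploratory and the remedy is cheap, this is a change the plan should make; it does not threaten the primary outcome.

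**What to change.** For the consolidation experiment under objective 5 in Section 5:
- Replace repeated-measures ANOVA with a linear mixed model: patient random intercept, fixed effects for condition and session order, fitted to every completed session from every patient.
- Report how many patients gave one, two or three conditions, and why the others stopped.
- Give the completer-only result as a sensitivity analysis.

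The session-order term is needed because 2.2.8 relies on a surprise memory test, and it can be a surprise only on the first visit. One-session patients are always first-visit patients. The term can separate order from condition only if the order of conditions differs between patients. Section 2.2.8 does not say how order is set, so the plan should state it.

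The cost is wording in Section 5; Python and MATLAB, the software already named there, both fit the model. No extra visits are needed. The downside is an assumption that stopping depends on observed data. If it depends on a patient's own unobserved response, bias is reduced but remains, which is why the counts, reasons and sensitivity analysis belong in the report.
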